In Part 1 of the study, participants will be enrolled sequentially into Cohorts 1, 2 and 3 (n=20 each). Participants will be recruited to Cohort 1 first, then Cohort 2 and followed by Cohort 3. Participants will be randomized (9:1 Active vs Active Control [AC]) according to a pre-generated randomization schedule to receive two Q4W injections of CAB 400 mg/mL 4 weeks apart (600 and 400 mg respectively) IM (n=18, *gluteus medius*, Cohort 1), SC (n=18, abdominal, Cohort 2) and IM (n=18, lateral thigh/*vastus lateralis*, Cohort 3) or two Q4W injections of CAB 200 mg/mL 4-weeks apart as active

controls (n=2 in each cohort). Cohorts 1-3 in Part 1 will each have a total of 20 participants (18 active and 2 active control) with a view to a minimum of 15 participants having evaluable data following both injections. All injections will be administered by an HCP. In Cohorts 1 and 3 the active control of CAB 200 mg/mL will be matched for dose e.g. 600 mg and 400 mg. In Cohort 2, subcutaneous dosing of active control (CAB 200 mg/mL) will be matched to the volume of CAB 400 mg/mL formulation administered.

The requirement for an optional Cohort 4 and determination of the dose and dosing schedule will be determined based on a review of the safety and tolerability data and any available PK data from Cohorts 1-3. This determination will be undertaken by the Study Team safety & PK Review (STR) and will be based on the comparison to historical PK data of the CAB 200 mg/mL formulation from the Phase 2/3 program. Cohort 4, if required, will assess the PK, safety and tolerability of alternative doses and/or dosing via SC and/or IM routes among 20 participants (18 active and 2 active control).

At the 22 December 2020 STR meeting, it was agreed to conduct Cohort 4 evaluating two Q4W injections of CAB 400 mg/mL 4 weeks apart (n=18, first injection 400 mg IM *gluteus medius* and second injection 200 mg SC) or two Q4W injections of CAB 200 mg/mL 4 weeks apart as active controls (n=2, first injection 400 mg IM *gluteus medius* and second injection 100 mg SC).

Cohort 4b, has been added to the study as part of protocol amendment 5. Cohort 4b will assess the PK, safety and tolerability of alternative doses via the SC route among 24 participants. All participants will receive two injections of 300 mg of CAB 400 mg/mL 4 weeks apart. CCI [REDACTED]

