Injections sites: vastus lateralis (IM lateral thigh injections and subcutaneous tissue (abdominal wall))	
Intramuscular CAB injections into the thigh (vastus lateralis) have not previously been administered in the CAB development program. Similar to the ventrogluteal region, the vastus lateralis is free of major nerves and blood vessels. Therefore, it is expected to be a safe site for injections. The vastus lateralis is part of a large muscle group and can tolerate high volume injections of up to 5 ml [Rodger, 2000] in adults with lesser amounts being stipulated in younger participants or in those with less developed or atrophied muscle beds [Rodger, 2000].
 
Subcutaneous tissue is frequently used for the administration of medications and is considered safe for injections in particular due to the lack of significant vasculature or nerves. The tolerability and ISR profile of subcutaneous administration of CAB 200 mg/mL is broadly similar to that following IM injections albeit with limited numbers of participants receiving SC injections. The incidence of nodules and erythema was higher with SC versus IM administration however these were mild in severity
	
Training of the appropriate technique will be provided to staff at the study centre and will be described in the study reference manual.
 
Any participants experiencing a grade 3 or higher AE event prior to the follow-up phase will withdraw from the study and enter the follow-up phase if i) the AE is considered related to IP in the opinion of the investigator and sponsor and ii) the investigator and sponsor agree the subject should be withdrawn from the study
 
Criteria for pausing recruitment or dosing of a cohort: If greater than 40% participants within a single cohort experience a local injection site reaction of at least grade 2 in severity once at least half of participants have received one or more injections.
 
If ≥20% of injections given within a single cohort are followed by an injection site reaction of at least grade 3 in severity (once half of cohort participants have received one or more injections).

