- Any participant developing a grade 2 or higher rash with concurrent fever, AST/ALT elevation or eosinophilia prior to the follow-up phase will be withdrawn from study intervention.

During the injection phase of the study, reasons for pausing recruitment or dosing of a cohort following review of safety data or Study Team Review are outlined below. Approval to recommence recruitment to or dosing of a cohort following a pause would be given by the ViiV Healthcare Safety and Labelling Committee (VSLC). In the event of a pause of dosing in the injection phase, the washout period may be extended if deemed necessary by the investigator and sponsor.

- 25% of participants receiving GSK1265744 have a grade 3 or higher AE or laboratory abnormality (with the exception of asymptomatic Grade 3 or higher cholesterol, triglyceride or CPK increase) prior to the follow-up phase or a \geq Grade 2 rash with concurrent fever, AST/ALT elevation or eosinophilia prior to the follow-up phase, where the AEs are considered related to IP in the opinion of the investigator and sponsor.

- If greater than 40% of injections administered within a single cohort are followed by a local injection site reaction of at least grade 2 in severity (once half of cohort participants have received one or more injections).¹⁷
- If $\geq 20\%$ of injections given within a single cohort are followed by an injection site reaction of at least grade 3 in severity (once half of cohort participants have received one or more injections).¹⁷
- If liver chemistry stopping criteria (see Section 7.1.1) are met in a participant in Cohort 5/6.
- If a Cohort 5/6 participant has abnormal liver chemistries not meeting protocol-specified stopping rules, the investigator believes study intervention discontinuation is in the best interest of the participant.
- If a Cohort 5/6 participant develops a grade 2 or higher rash with concurrent fever, AST/ALT elevation or eosinophilia prior to the follow-up phase and is withdrawn from study intervention.

During the long acting phase of the study reasons for stopping the study following Study Team Review are outlined below:

There is a participant death assessed as related to study drug by the principal investigator and sponsor.

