7.1.1. Liver Chemistry Stopping Criteria

Liver chemistry stopping, and increased monitoring criteria have been designed to assure participant safety and evaluate liver event etiology ([across oral and injection phases] in alignment with the FDA premarketing clinical liver safety guidance).

[figure not shown]
<http://www.fda.gov/downloads/Drugs/GuidanceComplianceRegulatoryInformation/Guidances/UCM174090.pdf>

Discontinuation of study intervention for abnormal liver tests is required when:

¹⁷ Where a cohort includes administration via different routes, the ISR data will be considered by each route of administration.

- a participant meets one of the conditions outlined in the algorithm
- in the presence of abnormal liver chemistries not meeting protocol-specified stopping rules, the investigator believes study intervention discontinuation is in the best interest of the participant.

Liver Chemistry Stopping Criteria – Liver Stopping Event Algorithm

Abbreviations: ALT = alanine transaminase; INR = international normalized ratio; SAE = serious adverse event; ULN = upper limit of normal.

Refer to [Appendix 6](#) for required Liver Safety Actions and Follow up Assessments.

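### The grade 2 injection-site-reaction pausing rule counts participants in Protocol 2.3.1 but injections in 7.1, so during second injections the two texts can disagree, in either direction

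*Protocol*

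**What the plan says.** The Section 2.3.1 risk table, in the row on injection sites, gives criteria for pausing recruitment or dosing of a cohort. The grade 2 criterion counts people: "If greater than 40% participants within a single cohort experience a local injection site reaction of at least grade 2 in severity". It becomes active "once at least half of participants have received one or more injections".

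Section 7.1 lists the pausing reasons again for the injection phase. Its grade 2 criterion counts injections: "If greater than 40% of injections administered within a single cohort are followed by a local injection site reaction of at least grade 2". It becomes active "once half of cohort participants have received one or more injections".

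The grade 3 criterion has a 20% threshold and counts injections in both places. In 2.3.1 it reads "of injections given within a single cohort are followed by an injection site reaction of at least grade 3 in severity".

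Footnote 17, attached to both injection-site-reaction criteria in 7.1, adds: "Where a cohort includes administration via different routes, the ISR data will be considered by each route of administration". The criteria in 2.3.1 carry no such note.

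For pausing criteria, Protocol Sections 4.1.2 and 10.5 and SAP Section 3.1 refer to Section 7.1. Under 7.1, a pause follows a review of safety data or a Study Team Review, and restarting needs approval by the sponsor's safety and labelling committee (VSLC).

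**The concern.** Both passages are current protocol text. They share the percentage, the grade and, in substance, the half-of-cohort starting point, but they count different things. Once some people have had two injections, the same data can meet one criterion and not the other.

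Section 2.3 names injection site reactions as the main safety concern of the study. Section 2.3.1 says that with the 200 mg/mL formulation they occur in most exposed participants, so a grade 2 threshold may well come into play. Participants are healthy volunteers with no expected benefit (Section 2.3.2), and a pause triggers a formal restart decision. Whether a pause has been reached should have one answer.

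**Working it through.** The protocol gives no operating figure for this rule, so there is none to reproduce. The check is a direct count under each text, with more than 40% read strictly.

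**Inputs**
- Cohort 4b: 24 participants, two subcutaneous injections each, four weeks apart (Protocol 4.1.1).
- Cohort 4: 20 participants, first injection intramuscular, second subcutaneous (Protocol 1.1 and 6.2.1).
- Cohort 4h: one injection per person (Protocol 4.1.1).
- Cohort 5: no second injection given, and Cohort 6 not needed (SAP 2.3).
- At the Cohort 1-5 interim analysis, only Cohort 4b still has injection-phase assessments outstanding (SAP 3.2).

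**Notation.** N people have been dosed and M of them have had a second injection. Of those dosed, r1 reacted to exactly one injection and r2 to both.
- Participant percentage = (r1 + r2) / N
- Injection percentage = (r1 + 2 × r2) / (N + M)

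**Before second injections.** M = 0 and r2 = 0, so both percentages equal r1 / N. The texts agree if the participant denominator is those dosed. This covers Cohort 4h throughout and Cohort 5 as run.

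**During second injections in Cohort 4b.** As an illustration, take N = 24 and M = 12, giving 36 injections.
- Participant threshold: 0.40 × 24 = 9.6, so 10 people.
- Injection threshold: 0.40 × 36 = 14.4, so 15 injections.

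| Reactions of grade 2 or higher | Participants | Injections | 2.3.1 | 7.1 |
|---|---|---|---|---|
| 10 people, one each | 10/24 = 41.7% | 10/36 = 27.8% | pause | no pause |
| 14 people, one each | 14/24 = 58.3% | 14/36 = 38.9% | pause | no pause |
| 15 people, one each | 15/24 = 62.5% | 15/36 = 41.7% | pause | pause |
| 9 people, both injections | 9/24 = 37.5% | 18/36 = 50.0% | no pause | pause |

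**Direction.** The participant percentage exceeds the injection percentage when (r1 + r2)(N + M) > (r1 + 2 × r2) N. This reduces to r2 / (r1 + r2) < M / N. At M / N = 12/24 = 0.5, the order reverses once more than half of the reactors have reacted twice.

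**Full dosing.** When M = N the participant percentage can never be the lower one. For 24 people the thresholds are 10 people and 20 of 48 injections. By then nothing is left to pause in that cohort, so this case does not measure the problem.

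**Undefined denominator.** Section 2.3.1 does not say whether its percentage is of those dosed or those enrolled. If 12 of 24 have been dosed once and 9 react, that is 9/12 = 75% of injections and of dosed participants, but 9/24 = 37.5% of those enrolled. On the enrolled reading, the texts can disagree even before second injections.

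**By-route note.** In Cohort 4, suppose 20 people have had the first injection, 10 the second, and 5 react to the second only. By route under 7.1 that is 5/10 = 50% of subcutaneous injections (pause). Under 2.3.1 it is 5/20 = 25% of participants (no pause). Cohort 4b uses one route, so the note does not affect it.

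**The case against.** The strongest reply is that Section 7.1 is the working reference. It is the discontinuation section, other sections cite it for pausing criteria, and the by-route note was added there. The liver row of the risk table also sends the reader to 7.1. The rule is applied at a data review rather than at the bedside. A reader might infer that staff have no means of telling which rule applies; the cross-references do not support that. What remains is that no clause gives 7.1 precedence and that the injection-sites row of 2.3.1 prints its own criteria without deferring. The SAP does not settle the unit either: Section 10.10.5 lists both subject-level and event-level injection-site-reaction tables.

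A reader might also infer that counting participants is always at least as cautious. That holds when everyone has had the same number of injections. It fails with uneven dosing, as the last row of the table shows.

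The reply that the live scope is narrow also stands. If the denominator is those dosed, only second injections are affected, and Cohort 4b is the cohort left. The size of the disagreement also depends on how reactions cluster within people, which the documents do not give.

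**Conclusion.** The inconsistency is real: one safety threshold is written with two units, and the protocol does not say which governs. At the illustrated stage of Cohort 4b, 10 to 14 people with one reaction each meet the 2.3.1 criterion only, while 9 people reacting to both injections meet the 7.1 criterion only. Neither text is always the stricter.

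The example assumes that all 24 have had the first injection and half the second, and that the participant denominator is those dosed. Other mixes shift the ranges. The conflict does not extend to the grade 3 rule, which counts injections in both sections. It also does not show that any past pausing decision was wrong, because the documents report no reaction counts. Part of the injection-site-reaction text in 2.3.1 is redacted and could not be checked, but the visible conflict does not depend on it.

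**What to change.** Reconcile Protocol Sections 2.3.1 and 7.1 so that both state the same unit, the same denominator (dosed or enrolled) and the same by-route convention. Alternatively, replace the criteria in 2.3.1 with a reference to 7.1. Use the agreed rule in the STR review outputs, showing numerator and denominator. The choice of rule belongs to the sponsor's safety committee, and this review does not favour either text. The cost is a short protocol clarification with no new data collection. It is most useful before further second injections in Cohort 4b.

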2.3.1.1. Other Clinically Relevant Information

Additional details concerning safety observations from clinical studies and for which a causal association has not been established or which are of minimal clinical significance may be found in the Investigator's Brochures [CAB IB 2021 ViiV Healthcare Document Number [RPS-CLIN-004375](#); [rHuPH20 IB](#), 2021]. Refer to 'Summary of data and guidance for the investigator'.

Seizure

Several cases of seizure have occurred during the CAB (200 mg/mL) program. These cases have had alternative explanations for their occurrence. Overall, there is not convincing evidence that cabotegravir exposure may be causally associated with seizure or with reduction of seizure threshold, due to the low frequency of reports, the confounders present in the cases received to date and lack of any pre-clinical signal or identified plausible mechanism. However, seizure and seizure-like events are considered as AEs of special interest for CAB. Participants with a prior history of seizure disorder will be excluded from study participation. Any cases of seizure or seizure like events will be reported within 24 hours of the event.

2.3.1.2. Non-Clinical Observations

Cabotegravir (200 mg/mL formulation) has undergone a comprehensive nonclinical toxicological evaluation in studies of appropriate design consistent with ICH requirements in the rat, monkey, mouse, and rabbit to support the clinical use of cabotegravir for the treatment of HIV infection. The CAB 400 mg/mL formulation was tested in a GLP rat study designed to assess local tolerability at the injection site when administered once per month for 3 months, and to assess potential systemic toxicity of the novel formulation containing Poloxamer 338. There were no cabotegravir-related effects on body weight or food consumption in rats. Injection site reactions included slight to marked oedema observed in both genders, slight to moderate erythema noted in females only and eschar (scabbing) observed in a small number of males and females. The ISRs were noted within 5 days of giving the injection, and, with time, decreased in incidence and severity, generally resolving at the next dosing occasion or by necropsy.

Non-clinical and clinical data regarding CAB plasma concentrations are discussed in Section [4.2.3](#). Non-clinical and clinical data regarding rHUPH20 are outlined in the IB [[rHuPH20 IB](#), 2021].

2.3.2. Benefit Assessment

This is a study in healthy adult participants and as such there is no expected benefit to administration of CAB. Participation in this study may contribute to the process of developing new therapies for HIV. There may be benefit to participants from the medical evaluations and assessments which could identify conditions that the participant was previously unaware.

2.3.3. Overall Benefit: Risk Conclusion

Taking into account the measures to minimise the risk to participants in this study, the potential risks identified with GSK1265744, 400 mg/mL and 200 mg/mL formulations and rHuPH20 are well understood and are justified by the anticipated benefits that may be afforded in the future to people living with HIV.

3. OBJECTIVES AND ENDPOINTS

Objectives	Endpoints
Primary	Primary

To describe the PK profiles of CAB 400 mg/mL formulation following multiple injections administered intramuscularly (gluteus medius or vastus lateralis) or subcutaneously (abdominal) in healthy adult participants
 
To assess the relative bioavailability of a CAB 400 mg/mL formulation administered via different routes (i.e., IM (vastus lateralis), IM (gluteus medius) or SC routes)
 
To compare exposures after CAB 400 mg/mL formulation administered via different routes with historical data of CAB 200 mg/mL formulation administered IM (gluteus medius)
	
Summary measures to include:
 
 • Maximum observed plasma concentration (C_{max}) [Injection 1 and 2] • Time of maximum observed plasma concentration (t_{max}) [Injection 1 and 2] • Area under the concentration – time curve for each injected dose from time zero to last quantifiable time point or 4 weeks following injection whichever is earlier (AUC_{0-t}) • Trough concentrations (C_τ) at 4 weeks following first injection (or earlier if the second injection occurs at <4-week interval) and 4 weeks following the second injection • Apparent terminal phase half-life (t_{1/2}) and absorption rate constant (K_{ALA}) [Injection 2] 
• Pair-wise comparisons of geometric mean ratios of plasma trough concentrations (C_τ), C_{max}, and Plasma AUC_{0-t} [injection phase] for Cohort 1, 2, 3, 4, 4b, and 4h
 
• Geometric mean ratios of plasma trough concentrations (C_τ) for Cohorts 1, 2, 3, 4, 4b, 4h, 5, and 6 (if conducted) compared to historical CAB 200 mg/ml data

Objectives	Endpoints
Safety	Safety

To assess safety and tolerability of CAB 400 mg/mL formulations following repeated intramuscular injections in the gluteus medius, vastus lateralis (lateral thigh) or subcutaneously (abdomen) of healthy adult participants
 
To assess safety and tolerability of CAB 200 mg/mL with rHuPH20 following a subcutaneous (abdominal) injection in healthy adult participants
 
To assess safety and tolerability of CAB 400 mg/mL with rHuPH20 following a subcutaneous (abdominal) injection in healthy adult participants
	
Safety and tolerability parameters including adverse events, clinical laboratory tests, and vital sign assessments

Secondary	Secondary

To assess the tolerability of CAB 400 mg/mL formulation following repeated intramuscular injections in the gluteus medius, vastus lateralis (lateral thigh) or subcutaneously (abdomen) of healthy participants
 
To assess the tolerability of CAB 200 mg/mL formulation with rHuPH20 following a subcutaneous (abdominal) injection in healthy adult participants
 
To assess the tolerability of CAB 400 mg/mL formulation with rHuPH20 following a subcutaneous (abdominal)
	
Tolerability parameters (adverse events) and liver biochemistry abnormalities

Objectives	Endpoints
injection in healthy adult participants	
PK	PK
Secondary	Secondary
To describe the PK profiles of CAB 200 mg/mL and CAB 400 mg/mL formulations with rHuPH20 following a subcutaneous (abdominal) injection in healthy adult participants	
Summary measures to include:
 
 • Maximum observed plasma concentration (C_{max}) • Time of maximum observed plasma concentration (t_{max}) • Area under the concentration – time curve from time zero to last quantifiable time point or 4 weeks following the injection whichever is earlier (AUC_{0-t}) • Trough concentrations (C_τ) through the Follow-up Phase • Apparent terminal phase half-life (t_{1/2}) and absorption rate constant (K_A)
To describe the pharmacokinetic (PK) profiles of oral CAB 30 mg following daily administration in healthy adult participant	
 • C_{max} • t_{max} • AUC(0-t) • C₂₄ • Day 29 C_τ

CCI

CCI

Objectives	Endpoints

 CCI 
	

4. STUDY DESIGN

4.1. Overall Design

This is a Phase I, double-blind (sponsor-unblind), active control, randomized, study to investigate the safety, tolerability and pharmacokinetics of repeat dose four-weekly (Q4W) and 12-weekly (Q12W) administration of long-acting CAB 400 mg/mL or CAB 200 mg/mL formulations. The data from active control (CAB 200 mg/mL) formulation in this study will be used for safety and tolerability comparisons only. These will be administered by HCPs intramuscularly (IM) or via subcutaneous (SC, abdominal) injections in healthy adult participants. We aim to recruit approximately 20% of women in this study.

The study will consist of:

- A 30-day Screening Period
- A 28-day oral lead-in (OLI), CAB 30 mg once daily with sparse PK sampling through Day 29
- A 7 to 14-day Washout Period (starting on Day 29)
- An Injection Phase
 - up to Week 8 (Injection 2 Day 28) in Part 1 Cohorts 1, 2, 3, 4 and 4b,
 - up to Week 4 (Injection Day 28) in Part 1 Cohort 4h and
 - up to Week 24 (Injection 2 Week 12) in Part 2 Cohorts 5 and 6 (if conducted)

- A 52-week Follow-up Phase post last injection or until CAB is no longer quantifiable (if this occurs prior to Week 52)

In circumstances where recruitment to or dosing of a cohort is paused, participants may be recruited or re-randomized (only prior to the injection phase) to subsequent cohorts if deemed appropriate by the investigator and sponsor.

If data following the conclusion of Part 1 or the interim data from Part 2 (12-week PK data from Cohort 5) warrants the assessment of alternative dose(s) and/or dosing schedule additional cohort(s) will be added.

4.1.1. Part 1

Participants will be enrolled sequentially into 3 cohorts (n=20 each). Participants will be recruited to Cohort 1 first, then to Cohort 2 and followed by Cohort 3. Participants will be randomized (9:1 Active vs Active Control [AC]) according to a pre-generated randomization schedule to receive:

- Cohort 1 - two IM injections of CAB 400 mg/mL or CAB 200 mg/mL (AC) formulations 4-weeks apart (600 mg and 400 mg respectively) in *gluteus medius*
- Cohort 2 - two subcutaneous injections of CAB 400 mg/mL formulation 4-weeks apart (600 mg and 400 mg respectively) or CAB 200 mg/mL (AC, 300 mg and 200 mg respectively) in the abdomen.

The VSLC agreed to reduce the dose of the second injection (see Section 6.2.1).

- Cohort 3 – two IM injections of CAB 400 mg/mL or CAB 200 mg/mL (AC) formulations 4-weeks apart (600 mg and 400 mg respectively) lateral thigh/*vastus lateralis*.

The STR agreed to reduce the dose of the first injection for the remaining Cohort 3 participants (see Section 6.2.1).

Cohort 4 (optional) - the requirement for an optional Cohort 4 and determination of the dose and dosing schedule will be determined based on an interim review of the safety and tolerability data from Cohorts 1-3 and PK data through Week 4 from Cohorts 1-2. This determination will be undertaken by the Study Team safety & PK Review (STR). This will be based on the comparison to historical PK data of the CAB 200 mg/mL formulation from the Phase 2/3 with the aim of selecting a safe dose predicted to achieve approximately 95% of dosed participants having trough concentrations higher than the Phase 3 benchmark. Active control participants will receive CAB 200 mg/mL matched to the volume of CAB 400 mg/mL if administered subcutaneously. Should Injection 1 be administered via the IM route, active control participants will receive CAB 200 mg/mL matched on dose to CAB 400mg/mL. Note: A minimum of 15 participants in each cohort are required to have evaluable data for both injections.

At their meeting on 22 December 2020, the STR agreed to conduct Cohort 4 (see Section 6.2.1).

Cohort 4b – two subcutaneous injections of CAB 400 mg/mL formulation 4-weeks apart (each 300 mg) CCI

Participants (n=24) will be randomized in equal numbers according to a pre-generated randomization schedule to one of two sequences (i.e. 12 per sequence) of two treatments to be administered along with Injection 1 and Injection 2, respectively (see Section 1.2 Schema Part 1 [Cohort 4b]).

Cohort 4h – one subcutaneous injection in the abdomen with rHuPH20 followed by CAB 400 mg/mL formulation (400 mg) or CAB 200 mg/mL (400 mg). Instructions regarding drug preparation and administration are provided in the pharmacy manual.

Participants will be randomized to receive 5000 U of rHuPH20 followed by either CAB 200 mg/mL or CAB 400 mg/mL formulations at a dose of 400 mg (2 mL and 1 mL, respectively). Four sentinel participants (two each administered CAB 200 mg/mL and CAB 400 mg/mL formulations) will be followed clinically for 10 days after dose administration and if there are no significant safety concerns upon a 10-day review of safety data, the remaining 16 participants will be dosed with rHuPH20 plus either CAB 200 mg/mL or CAB 400 mg/mL.

If participants prematurely discontinue the study, additional replacement participants may be enrolled at the discretion of the Sponsor in consultation with the investigator.

4.1.2. Part 2

Part 2 will commence once data (trough concentrations (C_{τ}) and plasma AUC_{0-t} up to and including Week 8 following Injection 1 from all participants in Cohort 1, and available safety and tolerability collected from each cohort 1-3) are reviewed and compared to historical PK data of the CAB 200 mg/mL formulation from the Phase 2/3 program. The first injection in Part 2 Cohort 5 will be administered once safety and tolerability data observed within the first ten days after the first injection for at least 50% of Cohort 4 participants (n=10) have been reviewed by the STR. If pausing criteria due to ISRs (see Section 7.1) are met in Cohort 4, Cohort 5 will be paused until further discussion. The determination of the dose and dosing schedule will be governed by a Study Team safety & PK Review (STR) with the aim of selecting a safe dose predicted to achieve approximately 95% of dosed participants having trough concentrations higher than the Phase 3 benchmark.

The requirement for an optional Cohort 6 will be based upon a review of the safety, tolerability and PK data from Cohort 5 (12 weeks after injection 1) and available safety, tolerability and PK data from Cohorts 1-4 and comparison to historical PK data of the CAB 200 mg/mL formulation from the Phase 2/3 program. This determination will be undertaken by the STR and will be guided by the predicted proportion of participants exceeding the phase 3 (CAB 200 mg/mL) trough concentration benchmark in simulation models and the ISR profile.

Participants in Cohorts 5 and 6 (n=22 each) will receive two IM injections 12 weeks apart, via the *gluteus medius*. Participants randomized to the active arm in Cohort 5 will receive ≤ 1200 mg (3 mL) of the CAB 400 mg/mL formulation. Participants randomized to the active arm in Cohort 6 will receive ≤ 2000 mg (5 mL) of the CAB 400 mg/mL formulation. A minimum of 16 participants in each cohort are required to have evaluable data for both injections.

The first four subjects enrolled in each cohort will serve as sentinel participants with three receiving CAB 400 mg/mL formulation (dose up to 1200 mg based upon data from Part 1) and one receiving active control (based on 3:1 randomization). These sentinel participants will be followed clinically for 10 days after dose administration to monitor the emergence of adverse events. If there are no significant safety concerns upon 10-day review of safety data (e.g. vital signs, ECGs, and adverse events) for the sentinel participants, the remaining participants will subsequently be treated with either CAB 400 mg/mL formulation (n=17) or AC (n=1) based on a 17:1 randomization. Dose administration for these remaining participants (n=18) will be staggered:

- a further 7 participants will be randomized and have their first injection.
- Following a review of safety data from the initial 7 participants 10 days post first injection, the remaining 11 participants will receive their first injection.
- These remaining participants may start the OLI phase prior to the 10-day reviews of safety data but they may only be randomized and proceed to the injection phase following the relevant safety review and if there are no significant safety concerns. Intramuscular dosing of active control (CAB 200 mg/mL) will be matched to the volume of CAB 400 mg/mL formulation administered via the *gluteus medius*.

The dose of the second injection in Cohort 5 will be guided by safety and PK data when $\geq 50\%$ participants in Cohort 5 complete Injection 1 Week 4 assessments.

If participants prematurely discontinue the study, additional replacement participants may be enrolled at the discretion of the Sponsor in consultation with the investigator.

